**Table H2      RECIST Evaluation of Target Lesions**

Complete response (CR)	Disappearance of all TLs since baseline. Any pathological lymph nodes selected as TLs must have a reduction in short axis diameter to < 10 mm.
Partial response (PR)	At least a 30% decrease in the sum of diameters of TLs, taking as reference the baseline sum of diameters.
Stable disease (SD)	Neither sufficient decrease in the sum of diameters to qualify for PR nor sufficient increase to qualify for PD.
Progression of disease (PD)	At least a 20% increase in the sum of diameters of TLs, taking as reference the smallest previous sum of diameters (nadir)—This includes the baseline sum if that is the smallest on study. In addition to the relative increase of 20%, the sum must demonstrate an absolute increase of at least 5 mm from nadir.
Not evaluable (NE)	Only relevant if any of the TLs at follow-up were not assessed or NE (eg missing anatomy) or had a lesion intervention at this visit. Note: If the sum of diameters meets the PD criteria, PD overrides NE as a TL response.
Not applicable (NA)	Only relevant if no TLs present at baseline.

CR = Complete response; NA = Not applicable; NE = Not evaluable; PD = Progression of disease; PR = Partial response; RECIST = Response Evaluation Criteria in Solid Tumours; SD = Stable disease; TL = Target lesion.

### **H 2.9.2      RECIST 1.1 NTL Assessment at Follow-up**

All other lesions (or sites of disease) not recorded as TL should be identified as NTLs at baseline. Measurements are not required for these lesions, but their status should be followed at subsequent visits. At each visit an overall assessment of the NTL response should be recorded by the investigator.

To achieve ‘unequivocal progression’ on the basis of NTLs, there must be an overall level of substantial worsening in non-target disease such that, even in presence of SD or PR in TLs, the overall tumour burden has increased sufficiently to merit unequivocal progression by NTLs. A modest ‘increase’ in the size of one or more NTLs is usually not sufficient to qualify for unequivocal progression status. The designation of overall progression solely on the basis of change in non-target disease in the face of SD or PR of target disease will therefore be extremely rare.

**Table H3      RECIST 1.1 Evaluation of Non-target Lesions**

Complete response (CR)	Disappearance of all NTLs since baseline. All lymph nodes must be non-pathological in size (< 10 mm short axis).
Non CR/Non PD	Persistence of 1 or more NTLs.
Progressive Disease (PD)	Unequivocal progression of existing NTLs. Unequivocal progression may be due to an important progression in 1 lesion only or in several lesions. In all cases the progression MUST be clinically significant for the physician to consider changing (or stopping) therapy.
Not evaluable (NE)	Only relevant when 1 or some of the NTLs were not assessed and, in the investigator's opinion, they are not able to provide an evaluable overall NTL assessment at this visit.  Note: For patients without TLs at baseline, this is relevant if any of the NTLs were not assessed at this visit and the progression criteria have not been met.
Not applicable (NA)	Only relevant if no NTLs present at baseline.

CR = Complete response; NA = Not applicable; NE = Not evaluable; NTL = Non-target lesion;  
PD = Progression of disease; RECIST = Response Evaluation Criteria in Solid Tumours; TL = Target lesion.

### H 2.9.3      RECIST 1.1 NL Identification at Follow-up

Details, including the imaging modality, the date of scan, and the location of any NLs will also be recorded in the CRF. The presence of one or more NLs is assessed as progression. The finding of an NL should be unequivocal, ie, not attributable to differences in scanning technique, change in imaging modality or findings thought to represent something other than tumour. If an NL is equivocal, for example because of its small size, the treatment and tumour assessments should be continued until the previously (pre-existing) new lesion has been assessed as unequivocal at a follow-up visit, and then the progression date should be declared using the date of the initial scan when the NL first appeared.

A lesion identified at a follow-up assessment in an anatomical location that was not scanned at baseline is considered an NL and will indicate PD.

### H 2.9.4      RECIST 1.1 Evaluation of Overall Visit Response at Follow-up

Derivation of overall visit response as a result of the combined assessment of TLs, NTLs, and NLs uses the algorithm shown in [Table H4](#).

**Table H4      RECIST 1.1 Overall Visit Response**

Target lesions	Non-target lesions	New lesions	Overall visit response
CR	CR	No	CR
CR	NA	No	CR
CR	Non-CR/Non-PD	No	PR
CR	NE	No	PR
PR	Non-PD or NE or NA	No	PR
SD	Non-PD or NE or NA	No	SD
NE	Non-PD or NE	No	NE
PD	Any	Yes or No	PD
Any	PD	Yes or No	PD
Any	Any	Yes	PD

Note: An overall assessment of CR (all other disease disappears/reverts to normal) would be changed to PR if ascites remains present radiologically.

CR = Complete response; NA = Not applicable (only relevant if there were no non-target lesions at baseline, however at least one target lesion is an entry criterion for the study); NE = Not evaluable; PD = Progression of disease; PR = Partial response; RECIST = Response Evaluation Criteria in Solid Tumours; SD = Stable disease.

The following overall visit responses are possible depending on the extent of tumour disease at baseline:

- For patients with TLs (at baseline): CR, PR, SD, PD, or NE
- For patients with NTLs only (at baseline): CR, Non-CR/Non-PD, PD, or NE
- For patients with no disease at baseline: NED (available as an option in the eCRF), PD, or NE

### **H 2.9.5      Central Imaging**

Images, including unscheduled visit scans, will be collected on an ongoing basis and sent to an AstraZeneca-appointed imaging CRO for quality control, storage, and for BICR. Guidelines for image acquisition, de-identification, storage of digital copies at the investigative site (as source documents), and transfer to the imaging CRO will be provided in a separate document. Electronic image transfer from the sites to the imaging CRO is strongly encouraged. A BICR of images will be performed at the discretion of AstraZeneca. Results of these independent reviews will not be communicated to investigators, and results of investigator RECIST 1.1 assessments will not be shared with the central reviewers. The management of patients will be based in part upon the results of the RECIST 1.1 assessment conducted by the investigator. Further details of the BICR will be documented in the Independent Review Charter.

## Appendix I Dose Modifications for the Management of Adverse Events

### I 1 Management of Study Treatment-related Toxicities

The patient will be continuously evaluated for AEs during the study. AEs are to be assessed according to the NCI CTCAE Version 5.0. The investigator should attribute the AE to a specific drug or to the combination if it is not possible to assign the AE to a specific study intervention. This is to guide dose modifications that may lead to a treatment hold, dose reduction and/or discontinuation of a specific study intervention. If there are multiple or overlapping toxicities or where the relationship is not clear, the investigator should consult with the AstraZeneca Study Team.

Dose modification guidelines for toxicities related to osimertinib and savolitinib are shown in [Table I1](#) and toxicities that require permanent discontinuation of study treatment are shown in [Table I2](#).

**Table I1 Study Treatment Dose Modification Instructions for Toxicities Related to Osimertinib and/or Savolitinib (excluding toxicities that require specific management guidelines)**

CTCAE Grade a	Instructions for osimertinib	Instructions for savolitinib
Grade 2 or lower	Continue and treat with supportive measures (as per local practice)	Continue and treat with supportive measures (as per local practice)
Grade 3	
Withhold osimertinib for up to 3 weeks
 
If the AE improves to ≤ Grade 2 after withholding of osimertinib for up to 3 weeks, osimertinib may be restarted at the same dose CC1 or a lower dose CC1.
 
If the AE does not improve to ≤Grade 2 after withholding for up to 3 weeks, permanently discontinue osimertinib.
 
See also toxicity specific guidance.
	
Withhold savolitinib
 
Savolitinib may be restarted at the same dose or consider a dose reduction upon recovery of the AE to ≤ Grade 2 within 7 days b
 
Savolitinib should be permanently discontinued if the AE does not recover to ≤Grade 2 within 7 days.
 
If this is a recurrence of the same Grade 3 toxicity, resume dosing at one reduced dose level (maximum of 2 dose reductions) as clinically appropriate upon recovery of the AE to ≤ Grade 2 within 7 days b

**Table I2 Toxicities that Require Permanent Discontinuation of Study Treatment**

Toxicity	Instructions for osimertinib	Instructions for savolitinib
Pulmonary: Interstitial lung disease or pneumonitis	Permanently discontinue osimertinib	Not applicable
Cardiovascular: QTc interval prolongation with signs/symptoms of serious arrhythmia	Permanently discontinue Osimertinib	Permanently discontinue savolitinib
Symptomatic congestive heart failure	Permanently discontinue osimertinib	Not applicable
Hepatic	Not applicable	See Section I 3.2 for drug-related hepatotoxicity meeting the criteria for discontinuation
Dermatological	Withhold osimertinib for suspected cases of SJS or EMM. Permanently discontinue osimertinib for confirmed cases of SJS or EMM.	Discontinue in the case of confirmed or suspected SJS
Acute hypersensitivity	Not applicable	Discontinue in the case of acute hypersensitivity

EMM = Erythema Multiforme Major; QTc = corrected QT interval; SJS = Stevens-Johnson syndrome.

Patients experiencing ILD will not be permitted to restart osimertinib. Patients experiencing QTc prolongation with signs/symptoms of serious arrhythmia will not be permitted to restart study treatment.

## I 1.1 Guidelines for the Management of Overlapping Toxicities Between Osimertinib and Savolitinib

### QTc Prolongation

QTc prolongation is a recognised toxicity of osimertinib and savolitinib; management of this toxicity is summarised in [Table I3](#).

**Table I3 Management of QTc Prolongation**

CTCAE Grade	Instructions for osimertinib	Instructions for savolitinib	Further investigation required
CTCAE Grade 1 or Grade 2	No action required	No action required	Review concomitant treatments and co-morbidities for risks of QT prolongation or risk for TdP a
CTCAE Grade 3 (QTc interval > 500 msec or > 60 msec change from baseline on at least 2 separate ECGs)	Withhold osimertinib until QTcF interval is < 481 msec, or has recovered to baseline if baseline QTc was > 481 msec, within 21 days of interruption. Then restart osimertinib at a reduced dose CCI CCI at the discretion of the investigator, to allow for situations where causality in relation to osimertinib may be difficult to determine.	Withhold savolitinib until QTcF interval is < 481 msec. If the QTcF resolves to < 481 msec in 21 days, restart savolitinib at a reduced dose.	Review concomitant treatments and co-morbidities for risks of QT prolongation or risk for TdP a  Consult with cardiologist to validate ECG finding. Ensure cardiac surveillance and take actions in accordance with clinical standards. Regular ECGs performed until resolution to QTcF < 481 msec.
	If the QTcF does not resolve to < 481 msec in 21 days, discontinue osimertinib.	If the QTcF does not resolve to < 481 msec in 21 days, discontinue savolitinib.	Consult with a cardiologist for further management as clinically indicated.
CTCAE Grade 4 (TdP; polymorphic ventricular tachycardia; signs and symptoms of serious arrhythmia)	Discontinue osimertinib	Discontinue savolitinib	Consult with a cardiologist for further management as clinically indicated.

a For guidance regarding potential interactions with concomitant medications known to prolong the QT interval, see Section J 5.

CTCAE = Common Terminology Criteria for Adverse Events; ECG = Electrocardiogram; QTc = corrected QT interval; QTcF = QT interval calculated using Fridericia's correction; TdP = Torsades de Pointes.

In light of the potential for QT changes associated with osimertinib, and in accordance with GCP, it is recommended that correction of clinically significant electrolyte abnormalities (hypokalaemia, hypomagnesaemia, hypocalcaemia) to within normal ranges takes place prior to first dose and is monitored during treatment with osimertinib.

The QTc interval prolongation potential of savolitinib 600 mg was assessed in a thorough QT study in healthy volunteers. Analysis of the data showed that it was a positive study, as the upper bounds of the 2-sided 90% CI for the mean  $\Delta\Delta\text{QTcF}$  were up to 13.6 msec and 14 msec, at 4 hours and 5 hours, respectively. QTcF will be assessed frequently on triplicate ECG assessments performed at regular intervals throughout the study according to the SoA.

### Erythema Multiforme and Stevens-Johnson Syndrome

Case reports of EM (including Erythema Multiforme Major [EMM]) and SJS have been uncommonly and rarely reported, respectively, in association with osimertinib treatment. Before initiating treatment, patients should be advised of signs and symptoms of EM/EMM and SJS. If signs and symptoms suggestive of EM/EMM develop, close patient monitoring and drug interruption or discontinuation of osimertinib should be considered. If signs and symptoms suggestive of SJS appear, osimertinib should be interrupted or discontinued immediately.

A case of SJS has been reported in temporal association with savolitinib. Patients who show symptoms or signs suggesting emerging SJS while on study treatment (eg, progressive skin rash often with blisters or mucosal lesions) must discontinue savolitinib immediately and receive appropriate treatment. If emerging SJS is suspected, re-challenge with savolitinib must be avoided.

## **I 2 Osimertinib Dose Modification and Guidance**

Osimertinib management should be in accordance with the local label in the first instance.

If a patient experiences a CTCAE Grade 3 and/or unacceptable toxicity (excluding ILD, QTc prolongation, keratitis, and EMM/SJS) including a DLT not attributable to the disease or disease-related processes under investigation, dosing will be interrupted and supportive therapy administered as required in accordance with local practice/guidelines.

If a toxicity (excluding ILD, QTc prolongation, keratitis, and EMM/SJS) resolves or reverts to  $\leq$  CTCAE Grade 2 within 3 weeks of onset, treatment with osimertinib may be restarted at the same dose **CCI** or a lower dose **CCI** using the rules below for dose modifications (Table I4) and with discussion and agreement with the AstraZeneca Study Team Physician as needed. There will be no individual modifications to dose regimen in response to toxicity, only potential dose reduction or dose interruption.

If the toxicity (excluding ILD, QTc prolongation, keratitis, and EMM/SJS) does not resolve to  $\leq$  CTCAE Grade 2 after 3 weeks of withholding osimertinib, then the patient should be withdrawn from the study and observed until resolution of the toxicity (Table I1).

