## **7 DISCONTINUATION OF STUDY INTERVENTION AND PATIENT DISCONTINUATION/WITHDRAWAL**

### **7.1 Discontinuation of Study Intervention**

It may be necessary for a patient to permanently discontinue (definitive discontinuation) study intervention. If study intervention is permanently discontinued, the patient will remain in the study to be evaluated for survival.

Patients may be discontinued from study intervention in the following situations. Note that discontinuation from study intervention is NOT the same thing as a withdrawal from the study.

- Patient decision. The patient is at any time free to discontinue treatment, without prejudice to further treatment.
- Adverse events.
- Severe non-compliance with the CSP.
- Disease progression as per RECIST 1.1; unless the patient is randomised to savolitinib plus placebo, when cross-over to savolitinib plus osimertinib may be permitted.

- Patients incorrectly initiated on study medication.
- Pregnancy.
- Specific stopping criteria, ie, ILD, acute anaphylaxis or QTcF interval prolongation with signs/symptoms of serious arrhythmia.

See the SoAs ([Table 1](#) and [Table 2](#)) for data to be collected at the time of intervention discontinuation and follow-up and for any further evaluations that need to be completed.

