### **Continuing on Monotherapy**

If a patient discontinues osimertinib due to toxicity the patient may continue with savolitinib until progression.

If a patient discontinues savolitinib due to toxicity they may continue with osimertinib monotherapy until the Principal Investigator believes there is no further benefit (this may be beyond PD in the absence of clinical symptoms or signs indicating clinically significant PD; no decline in performance status; absence of rapid PD or threat to vital organs or critical anatomical sites [eg, central nervous system metastasis, respiratory failure due to tumour compression, spinal cord compression] requiring urgent alternative medical intervention; or no significant, unacceptable or irreversible toxicities related to study intervention), according to the SoAs ([Table 1](#) and [Table 2](#)).

Following PD, patients may continue on osimertinib monotherapy and continue with all safety assessments as per the SoAs ([Table 1](#) and [Table 2](#)). Savolitinib monotherapy (either if originally randomised to savolitinib plus placebo or after discontinuation of osimertinib if originally randomised to savolitinib plus osimertinib) post progression is not permitted.

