#### **7.1.2 Procedures for Discontinuation of Study Intervention**

The investigator should instruct the patient to contact the site before or at the time if any study intervention is stopped. A patient that decides to discontinue study intervention(s) will always be asked about the reason(s) and the presence of any AEs. The date of last intake of study intervention(s) should be documented in the eCRF. All study intervention(s) should be returned by the patient at their next on-site study visit or unscheduled visit. Patients permanently discontinuing study intervention should be given locally available standard of care therapy, at the discretion of the investigator.

Discontinuation of study intervention(s), for any reason, does not impact on the patient's involvement in the study. The patient should continue attending subsequent study visits and data collection should continue according to the CSP. If the patient does not agree to continue in-person study visits, a modified follow-up must be arranged to ensure the collection of endpoints and safety information. This could be a telephone contact with the patient, a contact with a relative or treating physician, or information from medical records. The approach taken should be recorded in the medical records. A patient that agrees to modified follow-up is not considered to have withdrawn consent or to have withdrawn from the study.

As a minimum, telephone contact should be made with the patient 28 days following the discontinuation of both study interventions to collect new AEs and follow up on any ongoing AEs and concomitant medications (including any subsequent cancer therapy, if appropriate). Refer to Section 8.3.2 for full details on AE recordings during follow-up.

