## 7.2 Patient Withdrawal from the Study

- A patient may withdraw from the study at any time at his/her own request, or may be withdrawn at any time at the discretion of the investigator for safety, behavioural, compliance or administrative reasons. This is expected to be uncommon.
- A patient who considers withdrawing from the study must be informed by the investigator about modified follow-up options (eg, telephone contact, a contact with a relative or treating physician or information from medical records).
- At the time of withdrawal from the study, if possible, an Early Study Intervention Discontinuation visit should be conducted, as shown in the SoAs (Table 1 and Table 2). See the SoAs for data to be collected at the time of study withdrawal and follow-up and for any further evaluations that need to be completed.
  - The patient will discontinue the study intervention and be withdrawn from the study at that time.
- If the patient withdraws consent for disclosure of future information, the sponsor may retain and continue to use any data collected before such a withdrawal of consent.
- If a patient withdraws from the study, it should be confirmed if he/she still agrees for existing samples to be used in line with the original consent. If he/she requests withdrawal of consent for use of samples, destruction of any samples taken and not tested should be carried in line with what was stated in the informed consent and local regulation. The investigator must document the decision on use of existing samples in the site study records and inform the Global Study Team.

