## 8.1 Efficacy Assessments

### 8.1.1 CT and MRI Scans Tumour Assessments (RECIST 1.1)

The RECIST 1.1 guidelines for measurable, non-measurable, TLs and NTLs and the objective tumour response criteria are presented in [Appendix H](#) of this CSP.

Baseline tumour assessments should include CT/MRI of chest and abdomen (including liver and adrenal glands) and should be performed within 28 days of randomisation, and ideally as close as possible to the start of study intervention. At screening the MRI/CT scans will include brain imaging for all patients. Those determined to have brain metastases will have their brain rescanned at all subsequent tumour assessments. Any other regions suspected, or with known metastasis at baseline, will be assessed by imaging and recorded at baseline. The same imaging modality used for baseline tumour assessment should be used for each subsequent follow-up assessment throughout the study if possible. Further details of the CT and MRI acquisition parameters will be documented in a separate image acquisition guidelines document.

Follow-up assessments should be performed Q6W ( $\pm 7$  days) after randomisation until Cycle 7 (up to 24 weeks), and then Q8W ( $\pm 7$  days) until objective PD as defined by RECIST 1.1 even if a patient discontinues treatment prior to progression (unless they withdraw consent). For patients who cross-over based on confirmed objective disease progression during the initial randomised treatment period (including patients who have already crossed over based on confirmed PD prior to CSP Version 3.0), scheduled RECIST 1.1 tumour assessments are not required, and the subsequent assessment of disease progression will be based on standard-of-care scan or investigator determined clinical progression. Scheduled RECIST 1.1 tumour assessments are required (the scan frequency is against initial randomisation) for patients who cross-over after study unblinding and who have not objectively progressed during the initial randomised treatment period. Patients who cross-over after study unblinding, who have no objective progression during initial randomisation period, and who discontinue study intervention after cross-over for reasons other than investigator-confirmed disease progression will continue scheduled RECIST 1.1 tumour assessments until objective disease progression per RECIST 1.1 as assessed by investigator, unless they withdraw consent to the entire study.

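### Appendix I 2 withdraws from the study a patient whose toxicity outlasts three weeks off osimertinib, while the rest of the protocol stops only the drug and keeps scanning to progression

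*Supplement*

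**What the plan says.** Appendix I 2 sets the rule for osimertinib toxicity that does not settle to Grade 2 or lower after three weeks of withholding: "then the patient should be withdrawn from the study and observed until resolution of the toxicity". ILD, QTc prolongation, keratitis and EMM/SJS are carved out. The sentence points to Table I1.

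The osimertinib column of Table I1, for Grade 3 toxicity that has not improved to Grade 2 or lower, reads "after withholding for up to 3 weeks, permanently discontinue osimertinib". It says nothing about study status.

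The main text treats stopping a drug and leaving the study as different things:

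- Section 7.1: "If study intervention is permanently discontinued, the patient will remain in the study to be evaluated for survival". It adds: "Note that discontinuation from study intervention is NOT the same thing as a withdrawal from the study".
- Section 7.1, Continuing on Monotherapy: "If a patient discontinues osimertinib due to toxicity the patient may continue with savolitinib until progression".
- Section 7.1.2, on stopping study intervention for any reason: "The patient should continue attending subsequent study visits and data collection should continue according to the CSP".
- Section 8.1.1: scans run "until objective PD as defined by RECIST 1.1 even if a patient discontinues treatment prior to progression", with withdrawal of consent as the only exception. Table 1 footnote o says the same in substance. Table 2 footnote h does so for patients who cross over after unblinding without having progressed.
- Section 7.2, on withdrawal from the study: "The patient will discontinue the study intervention and be withdrawn from the study at that time".

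**The concern.** One trigger leads to two different instructions. Under Table I1 and Sections 7 and 8 the patient stops osimertinib (or its placebo), may stay on savolitinib, and is scanned until progression. Under Appendix I 2 the patient leaves the study, which by Section 7.2 also ends study intervention.

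The difference matters for the endpoints. Section 9.4.2.2 defines PFS irrespective of withdrawal from therapy, so it depends on scans after discontinuation. If a site applies Appendix I 2 literally, those scans stop because of toxicity, a reason related to treatment and so not safely assumed to be uninformative about prognosis. A response that would have appeared later is not seen, and a patient whose toxicity is put down to osimertinib/placebo alone loses savolitinib that Section 7.1 would have allowed.

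**Working it through.** The plan has no figure to reproduce here. The check is a comparison of texts, followed by an illustrative size.

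**1. Is the wording current?** Yes. The Amendment 2 summary of changes records an edit to this very rule, moving the start of the three weeks from onset of toxicity to the time osimertinib was withheld. The edit kept the reference to withdrawal from the study, and the body of Appendix I 2 carries it.

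**2. Can the two instructions be reconciled?** Not on the text. Section 7.1 says the two terms differ, and Section 7.2 gives withdrawal its fuller meaning. Section 7.2 does let an investigator withdraw a patient for safety, but as a discretionary step expected to be uncommon. Appendix I 2 makes it the default. Observation until the toxicity resolves is not the same as scanning to progression.

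**3. What happens to each endpoint under a literal reading?**

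- *ORR (Section 9.4.2.1).* Data up to the last evaluable assessment are used, so a response already recorded still counts. Only later responses are lost.
- *PFS (Section 9.4.2.2).* The patient is censored at the last evaluable scan. Progression or death after two or more missed visits does not count. Two visits are about 2 × 6 = 12 weeks on the six-weekly schedule (to week 24) and 2 × 8 = 16 weeks on the eight-weekly schedule.
- *DoR (Section 9.4.2.2).* It takes over the PFS censoring, but exists only for responders. Only patients already in response when withdrawn are affected.
- *OS.* Section 7.3 seeks vital status for all randomised patients, and Section 8.1.2 includes those withdrawn from the study who have not withdrawn consent.

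**4. Illustrative size for ORR.** The documents give no rate of unresolved osimertinib toxicity. Inputs:

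- planned arm size 28 (Section 9.2), with the actual number smaller because recruitment stopped early;
- assumed share w of an arm withdrawn before any response: 2–10%;
- assumed response r on savolitinib alone: 5–10%, the two low scenarios for the savolitinib-plus-placebo arm in Section 9.5. This is the relevant rate because osimertinib is stopped under either text.

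Patients affected = 28 × w: 28 × 0.02 = 0.6 to 28 × 0.10 = 2.8.

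ORR loss = w × r: 0.02 × 0.05 = 0.001 (0.1 points) to 0.10 × 0.10 = 0.010 (1.0 point).

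Responders lost = 28 × w × r: 28 × 0.001 = 0.03 to 28 × 0.010 = 0.28. One responder is 1/28 = 3.6 points.

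Taking the highest Section 9.5 scenario, r = 43%, with w = 10% gives 0.10 × 0.43 = 4.3 points, or 28 × 0.043 = 1.2 responders.

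For given w and r these overstate the loss, because they assume every withdrawn patient could otherwise have stayed on savolitinib. Table I1 stops savolitinib permanently when Grade 3 toxicity related to it has not recovered to Grade 2 or lower within 7 days. Where the toxicity is also attributed to savolitinib, that drug would normally have stopped well before three weeks.

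**5. A related slip.** The restart sentence in Appendix I 2 still counts three weeks from onset, whereas its next paragraph and Table I1 count from withholding. A toxicity that settles more than three weeks after onset but within three weeks of withholding meets neither Appendix I 2 rule, although Table I1 allows a restart.

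**The case against.** The best defence is that the protocol corrects itself. The sentence cites a table that only stops the drug, asks for continued observation, and is outnumbered by Sections 7.1, 7.1.2 and 8.1.1. A patient withdrawn under Appendix I 2 has not withdrawn consent, so Section 8.1.1 read literally still requires scans. Section 8.2.6 also mixes discontinuation from the study with discontinuation from study intervention, which points to loose drafting rather than a different policy. The trigger is narrow, recruitment has ended, and Section 9.4.1.2 says the study is not designed to support labelling claims.

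Most of this stands, and it keeps the severity low. It does not rescue the sentence: that other sections override Appendix I 2 shows which text is wrong. A site managing a toxicity will consult the dose-modification appendix.

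A reader might infer more than the documents support:

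- *That the loss falls mainly on the combination arm.* The trigger is osimertinib toxicity, but there is no rate for either arm, and blinded investigators attribute events to osimertinib/placebo. Imbalance cannot be derived.
- *That OS is censored early.* Sections 7.3 and 8.1.2 still seek vital status after withdrawal.
- *That every withdrawn patient loses DoR or savolitinib.* DoR concerns only those already in response, and savolitinib only toxicity not also attributed to it.

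**Conclusion.** Wrong as written; low severity. The textual conflict is certain. Its effect depends on how many patients reach this trigger and how many sites follow Appendix I 2 rather than the main text, and the documents give neither.

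Under the stated assumptions the ORR loss is about 0.1–1.0 points, less than one responder per planned arm. Only the most generous pairing (10% withdrawn, 43% response) exceeds one. The clearer consequence is early PFS censoring for a treatment-related reason in whatever number of patients is withdrawn, which I leave unquantified.

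**What to change.** In Appendix I 2, replace the instruction to withdraw with: permanently discontinue osimertinib/placebo (Table I1) and observe until the toxicity resolves; the patient remains in the study for scheduled RECIST assessments to objective PD and for survival follow-up, and may continue savolitinib per Section 7.1 unless the savolitinib rules in Appendix I also stop it.

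In the restart sentence of the same section, count the three weeks from withholding instead of from onset, to match Table I1.

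The cost is a short protocol correction and a note to sites. No new data collection is needed, because Sections 7.1.2 and 8.1.1 already require the follow-up.
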